5.7. Requirements and Recommendations Regarding Specific Adverse Events or Conditions

5.7.1. Transaminase Elevations

Consistent with observations in a dog toxicology study, reversible asymptomatic ALT/AST increases were observed early in the idelalisib program in phase 1 studies (101-02 and 101-07) in subjects with hematologic malignancies. Transaminase elevations generally occurred within 4 to 12 weeks of drug initiation, and resolved spontaneously over a period of 2 to 4 weeks with drug being continued for Grade 1 and 2 elevations and drug withheld for Grade 3 or 4 elevations until resolution. These early observations are consistent with the ongoing experience with idelalisib treatment and transaminase elevations are now well characterized as most frequently asymptomatic, transient and occurring within the first 3 months of treatment.

Grade 1 or 2 elevations commonly resolve despite continued idelalisib treatment and Grade 3 or 4 elevations can be managed by temporarily withholding idelalisib. Successful rechallenge after resolution at either the same or lower dose level of idelalisib has been achieved in the majority of subjects. There has been no evidence of impaired synthetic function. Close monitoring of hepatic laboratory tests during therapy is important to allow for appropriate idelalisib interruption and reinstitution so that subjects may continue with study drug treatment.

Cholangitis manifest as hyperbilirubinemia out of proportion to serum transaminase elevations has been observed. While disease-related factors, neutropenia, toxicity from prior therapies, effects of ongoing supportive care, or pre-existing cholelithiasis may have initiated such events, it is possible that idelalisib played a contributory role. In such subjects, rechallenge with idelalisib has been possible and has not been associated with other severe adverse events.

In selected subjects who experience more complicated hepatic AEs, further workup may be warranted particularly in subjects who first experience a serum ALT/AST elevation ≥12 weeks from the start of study drug therapy, who have an elevation in serum bilirubin concentration or coagulation parameters, or who have other characteristics that suggest an atypical change in transaminase values. Hepatic AEs that require additional workup should be discussed with the Gilead Sciences Medical Monitor.

5.7.2. Gastrointestinal Events

Isolated cases of gastrointestinal inflammation (eg, stomatitis, colitis, cecitis) have been noted in subjects receiving idelalisib. Rare cases of gastrointestinal perforation have occurred, generally in the setting of occult carcinoma, mesenteric embolus or diverticular disease. Study treatment must be discontinued in subjects who experience bowel perforation.

For study subjects who develop severe abdominal pain the possibility of a bowel obstruction or perforation should be considered. Appropriate clinical and radiographic examination should be performed and supportive care or surgical intervention should be considered.

Subjects who have developed evidence of enteritis during idelalisib therapy have been successfully treated with antidiarrheals (eg, loperamide) and with enteric steroidal (eg, budesonide) or non-steroidal (eg sulfasalazine [Azulfidine[®]]) anti-inflammatory agents and have been able to continue or resume idelalisib.

[figure not shown]
For study subjects who develop persistent diarrhea, causes related to concomitant medications or gastrointestinal infections such as *Clostridium difficile* (particularly for patients recently treated with broad spectrum antibiotics), *Shigella*, *Campylobacter*, *Yersinia* and CMV should be considered and treated if appropriate. Depending upon the clinical circumstances, endoscopy and biopsy, with bacterial and viral immunohistochemical (IHC) staining should be considered. For Grade ≥ 3 or persistent Grade 2 colitis or diarrhea without clear etiology (eg, *C. difficile* enterocolitis), endoscopy with biopsy is strongly recommended. See Section 6.1.8.9 for required testing. In the event that an infectious cause is not identified, an antimotility agent (eg, loperamide) may lessen symptoms and intervention with enteric steroidal (eg, budesonide) or non-steroidal (eg, sulfasalazine) anti-inflammatory agents should be considered. In such subjects, rechallenge with idelalisib at a lower dose level has resulted in recurrence of symptoms in some but not all subjects and has not been associated with other severe adverse events.

Investigation for Idelalisib Late Onset or Severe Diarrhea/Colitis

See CTCAE Version 4.03 for definitions of colitis and diarrhea.

Among idelalisib-treated patients who reported diarrhea or colitis, the median time to onset of any grade diarrhea or colitis was 1.9 months (range, 0.0–29.8), of Grade 1 or 2 was 1.5 months (range, 0.0–15.2), and of Grade 3 or 4 was 7.1 months (range, 0.5–29.8). Kaplan–Meier curves of time to onset of diarrhea or colitis are shown for all idelalisib-treated patients in [Figure 5-1 {Coutre 2015}](#).

Figure 5-1. Kaplan-Meier Time to Diarrhea or Colitis

Idelalisib-associated severe diarrhea responds poorly to antiperistalsis agents, however, median time to resolution ranged between 1 week and 1 month across trials following interruption of idelalisib treatment and, in some instances, initiation of corticosteroid treatment {Gilead Sciences Inc 2014}

5.7.2.1. Required Assessments for Diarrhea/Colitis

For any grade diarrhea/colitis, obtain history of onset and duration of diarrhea, including description of number of stools and stool composition (eg, watery, bloody, nocturnal), travel history, dietary changes and a medication review to identify possible diarrheogenic agents; perform physical examination including assessment for fever, dizziness, abdominal pain/cramping, and weakness (ie, evaluate for sepsis, bowel obstruction, dehydration).

5.7.2.2. Recommended Assessments for Diarrhea/Colitis

Differentiation between small-bowel and large-bowel diarrhea may be possible on a clinical basis. If unclear, consider upper and lower tract endoscopy with biopsy.

- Small bowel diarrhea is characterized by large volume diarrhea (more than 1 per day), possible associated dehydration weight loss and periumbilical pain. Consider an endoscopic small-bowel biopsy and evaluate other etiologies such as celiac disease.
- Large-bowel diarrhea may present with lower pelvic pain, tenesmus, generally smaller stool volume with gross blood frequently found in the stool. Consider a colonoscopic evaluation and biopsy.

For Grade ≥ 3 or persistent Grade 2 colitis or diarrhea without clear etiology (eg, *C. difficile* enterocolitis), endoscopy with biopsy is strongly recommended. All biopsy samples should include immunohistochemistry and PCR for CMV, Adenovirus. If ileal biopsy is performed, consider Acid Fast Bacillus staining.

5.7.3. Dermatological Events

Subjects receiving idelalisib with \geq Grade 3 rash have generally presented with a maculopapular rash on the trunk and extremities that is occasionally associated with fever and/or pruritus and responded to treatment with diphenhydramine and/or topical or oral corticosteroids.

For subjects who develop a Grade \geq 3 rash for which an underlying etiology cannot be identified (eg, infection, co-suspect drug), study drug must be interrupted. Resumption of study drug should be considered once rash resolves.

Severe cutaneous reactions, including fatal events of Stevens-Johnson syndrome (SJS) and toxic epidermal necrolysis (TEN), have been reported in subjects receiving idelalisib.

Assessment of potential causal association between idelalisib and the occurrence of SJS or TEN has been confounded by the coadministration of antineoplastic agents (eg, bendamustine, rituximab) and/or other concomitant medications known to be associated with SJS or TEN (eg, allopurinol). If SJS or TEN is suspected, idelalisib must be discontinued and all coadministered medications associated with SJS or TEN should be interrupted, and the subject treated per institutional standards.

5.7.4. Pulmonary Events

Documented bacterial, fungal, viral, and pneumocystis pneumonias have been observed in patients receiving idelalisib, primarily in patients with CLL. Some study subjects receiving idelalisib alone or in combination have developed evidence of pneumonitis without documented pulmonary infection.

Given the potential for infectious or drug-related pulmonary adverse events, clinicians should be particularly observant for evidence of respiratory events in subjects participating in this trial. Subjects who describe pulmonary symptoms (eg, dyspnea on exertion, cough, shortness of breath); manifest a decline from baseline of $\geq 5\%$ in oxygen saturation, or demonstrate evidence of pulmonary inflammation (eg, focal or diffuse interstitial pattern or ground-glass opacities on chest CT) should be evaluated. Potential bacterial, fungal, or viral etiologies should be assessed. Noninfectious etiologies such as pulmonary edema or thromboembolism should also be considered.

As appropriate for the clinical situation and culture results, subjects should be treated empirically or given specific antibiotics, antifungals, or antiviral agents for a cultured organism. Supportive care, including oxygen or mechanical ventilation, should be provided as necessary.

For subjects with suspected Grade 1 pneumonitis, withhold idelalisib until resolution to baseline. Upon resolution to baseline, idelalisib may be resumed at lower dose level or discontinued at investigator discretion. For subjects with suspected Grade ≥ 2 pneumonitis (eg, new onset or worsening of baseline cough, dyspnea, hypoxia and/or a diffuse interstitial pattern or ground-glass opacities on chest imaging without obvious infectious etiology), idelalisib must be discontinued permanently and therapy initiated as clinically appropriate.

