5.6. Safety Monitoring and Study Drug Interruption/Dose Modification/Discontinuation

Required and recommended actions for discontinuation or dose modification for both drugs, including the combination regimen, are provided in [Table 5-3](#). The requirements and recommendations are based on the drug and the CTCAE grade of specific toxicities, focusing on the types of events most commonly attributed to each of the study agents.

In cases of uncertainty, the study medical monitor should be contacted.

There is no limit on the length of time either idelalisib or BI 836826 may be held during the study (eg, to allow resolution of toxicity). If both idelalisib and BI 836826 are held during the same period, when appropriate both drugs should be restarted on the same day rather than dosing with idelalisib for 7 days prior to restarting BI 836826. During the combination therapy period (through Week 46), if either study drug is permanently discontinued, the other study drug should also be permanently discontinued. See Section [6.6.1](#) for recommended follow-up.

Table 5-3. Requirements and Recommendations for Discontinuation or Modification of Study Treatment in Response to Adverse Events

NCI CTCAE Grade ¹	Idelalisib	BI 836826
HEMATOLOGICAL ADVERSE EVENT		
Neutropenia		
Grade ≤ 2 neutropenia	Maintain current dose and schedule.	Maintain current dose level and schedule.
Grade 3 neutropenia	Required action: Blood counts must be monitored at least weekly until neutropenia Grade ≤ 2 .	Maintain current dose level and schedule. Consider G-CSF support. If febrile neutropenia not resolving within 48 hrs with appropriate treatment, decrease subsequent dose by 50% ² .
Grade 4 neutropenia (or occurrence of neutropenic fever or infection)	Required action: Interrupt idelalisib. Blood counts must be monitored at least weekly until neutropenia is \leq Grade 2. Recommended action: May resume idelalisib at lower dose level when neutropenia is Grade ≤ 3 ² . Neutropenia should be managed according to established clinical guidelines.	If Gr 4 neutropenia lasts >7 days, or febrile neutropenia not resolving within 48 hrs with appropriate treatment, decrease subsequent dose by 50% ³ Otherwise, maintain current dose level and schedule and consider G-CSF support.
Thrombocytopenia		
Grade ≤ 2 thrombocytopenia	Maintain current dose and schedule.	Maintain current dose level and schedule.

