Grade 4 (ALT/AST > 20 × ULN; Bilirubin > 10xULN)	Required action: Withhold idelalisib. Monitor ALT, AST, ALP, and bilirubin at least 1x per week until all abnormalities are Grade ≤1. If bilirubin abnormality was Grade 4, discontinue idelalisib. Recommended action: If bilirubin abnormality was Grade <4 resume idelalisib at lower dose level ² .	Withhold BI 836826. Monitor ALT, AST, ALP, and bilirubin at least 1x per week until all abnormalities are Grade ≤1. If bilirubin abnormality was Grade 4, discontinue BI 836826.
Pneumonitis (with new onset or worsening of baseline dyspnea, cough, or hypoxia without obvious infectious cause)		
Grade 1 (asymptomatic)	Required action: Withhold idelalisib until resolution to baseline. May resume at lower dose level or discontinue at investigator discretion.	Maintain current dose level and schedule.
Grade ≥ 2	Required action: Discontinue idelalisib permanently in subjects with any severity of symptomatic pneumonitis and institute therapy as clinically appropriate.	Discontinue BI 836826.
Pneumocystis jirovecii pneumonia (PJP)		
Any Grade	Required action: Discontinue idelalisib.	Discontinue BI 836826.
CMV Infection/Reactivation⁴		
Any Grade	Required action: Interrupt idelalisib upon unequivocal clinical or laboratory evidence of CMV infection. Treat according to established clinical guidelines. If the benefits of resuming idelalisib are judged to outweigh the risks, consider pre-emptive CMV therapy.	Discontinue BI 836826.
Hepatitis B Reactivation		
Any Grade	Required action: Discontinue idelalisib.	Discontinue BI 836826.

NCI CTCAE Grade ¹	Idelalisib	BI 836826
OTHER NONHEMATOLOGICAL ADVERSE EVENTS		
Grade ≤ 2	Maintain current dose level and schedule.	Maintain current dose level and schedule.
Grade ≥ 3	Withhold study drug until Grade ≤ 1. May resume study drug at initial or next lower dose ² or discontinue study drug at investigator discretion.	Withhold study drug until Grade ≤ 1. May resume study drug at initial or at 50% ³ or discontinue study drug at investigator discretion.

1. CTCAE, Version 4.03.
2. If assigned idelalisib dose level is 50 mg BID, dose reduction is not possible and idelalisib should be interrupted.
3. Dose reduction of BI 836826 by 50% may be performed twice. If still not tolerated, BI 836826 should be discontinued.
4. CMV should be diagnosed using clinical or laboratory criteria per established institutional standard

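### Protocol Section 5.7.4 and Table 5-3 can be read to put an asymptomatic, imaging-only pneumonitis finding in different grades, and the grade decides whether both study drugs must be stopped.

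*Protocol*

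**What the plan says.** Protocol Section 5.7.4 (Pulmonary Events) has a rule for each grade. For the lower grade: "For subjects with suspected Grade 1 pneumonitis, withhold idelalisib until resolution to baseline". After that the investigator may restart the drug at a reduced dose or stop it. The section does not describe what Grade 1 looks like. For the higher grade it offers new or worse respiratory symptoms as examples and then goes on: "and/or a diffuse interstitial pattern or ground-glass opacities on chest imaging without obvious infectious etiology), idelalisib must be discontinued permanently". Its pneumonitis rules name no action for BI 836826.

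Table 5-3 (Protocol Section 5.6) opens its block with the heading "Pneumonitis (with new onset or worsening of baseline dyspnea, cough, or hypoxia without obvious infectious cause". The first row is Grade 1, labelled asymptomatic. For idelalisib it requires: "Withhold idelalisib until resolution to baseline. May resume at lower dose level or discontinue at investigator discretion". BI 836826 is kept at its current dose and schedule. The Grade ≥ 2 row ties permanent discontinuation of idelalisib to symptomatic pneumonitis of any severity, and BI 836826 is discontinued.

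The text of Section 5.6 links the two drugs through Week 46: "if either study drug is permanently discontinued, the other study drug should also be permanently discontinued". Section 6.6.1 repeats the link.

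**The concern.** The split between Grade 1 and Grade ≥ 2 separates a temporary hold from a mandatory permanent stop. Table 5-3 draws that line by symptoms. The examples in Section 5.7.4 draw it by symptoms, imaging, or both. A subject with no symptoms but with ground-glass opacities or a diffuse interstitial pattern, and no evident infection, falls where the two lines may differ.

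At stake is whether the subject must come off both drugs permanently or may stay on BI 836826 while idelalisib is held. The classification an investigator adopts may also colour the grade recorded for the event, and safety is all that the terminated study still assesses.

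**Working it through.** No arithmetic applies, and the plan gives no figure to reproduce. The check sets the provisions side by side and follows one presentation through them.

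**Step 1. Compare the actions grade by grade.**

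| | Section 5.7.4 | Table 5-3 |
|---|---|---|
| Grade 1, description | none given | asymptomatic |
| Grade 1, idelalisib | hold to baseline, then restart lower or stop at discretion | the same |
| Grade 1, BI 836826 | not stated | unchanged |
| Grade ≥ 2, description | examples: symptoms and/or imaging pattern | symptomatic, any severity |
| Grade ≥ 2, idelalisib | permanent stop | permanent stop |
| Grade ≥ 2, BI 836826 | not stated | stop |

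The idelalisib actions match. The difference lies in the description rows and in the silence of Section 5.7.4 on BI 836826.

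**Step 2. Classify the test case.** Take a subject in the combination period with no respiratory symptoms or hypoxia, and with ground-glass opacities or a diffuse interstitial pattern that has no obvious infectious cause.

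- By the row labels of Table 5-3, this is Grade 1.
- By the examples in Section 5.7.4, the ordinary sense of and/or lets the imaging finding stand alone, so the case can be read as suspected Grade ≥ 2.
- By the Grade 1 sentences of Section 5.7.4, the case would be handled as in the table if the investigator had already called it Grade 1. Nothing in the section tells the investigator to do so.

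**Step 3. Follow each classification through to both drugs.**

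- Grade ≥ 2: idelalisib must stop permanently. BI 836826 then stops as well, through the link in Section 5.6 or directly through the Grade ≥ 2 row of the table.
- Grade 1: idelalisib is held. Later restart at a lower dose is optional, and so is stopping. BI 836826 continues, unless the investigator chooses to stop idelalisib permanently, in which case the link in Section 5.6 again applies.

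The outcomes can coincide, but one route requires both drugs to stop and the other does not.

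**Step 4. Test the table heading against its rows.** The heading confines the block to pneumonitis with new or worse dyspnea, cough or hypoxia. The first row is for subjects without symptoms. On a literal reading the heading excludes most or all of what that row covers. This mismatch stands however Section 5.7.4 is read.

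**Step 5. Look for a rule that settles it.** Footnote 1 of Table 5-3 and Section 7.2.2 refer grading to CTCAE 4.03. No text says whether that scale, the table label or the examples in Section 5.7.4 prevail when they point different ways. Section 5.6 sends uncertain cases to the medical monitor, which helps only if the reader notices the uncertainty.

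**The case against.** The strongest case on the other side is that Section 5.7.4 has its own Grade 1 rule, identical to the table for idelalisib. The imaging text is a list of examples, not a definition, and severity is graded by CTCAE. Read as a whole, an asymptomatic case would be Grade 1 in both places. This is a fair reading, and it rules out saying that Section 5.7.4 simply requires a permanent stop for every such scan. It does not remove the ambiguity. A listed example is still offered as an instance of its category, this category carries a mandatory action, and Section 5.7.4 never says what Grade 1 is.

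A reader might infer more than the documents support:

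- *That the per-grade rules for idelalisib conflict.* They do not (Step 1). Nor does the table order a restart: it allows one, at a lower dose, and equally allows stopping.
- *That any interstitial change triggers the stop.* The Grade ≥ 2 example names a diffuse pattern. A focal pattern appears only in the earlier sentence on who should be evaluated.
- *That this earlier sentence is a further conflict.* Evaluation comes before grading and is compatible with either outcome.
- *That the table heading sends the case to the catch-all rows for other non-hematological events, with both drugs maintained.* Pneumonitis has its own block with an explicit asymptomatic row, so this is strained.
- *That sites will demonstrably diverge, or that both enrolled subjects are certain to be affected.* The documents do not say how many sites treat the two subjects. Under Section 6.2.1, study scans have ended and imaging is at the investigator's discretion under standard of care.
- *That the reported safety analysis will be distorted.* The SAP grades adverse events by CTCAE (Section 7.1.2), only lists them (Sections 7.1.6 and 7.7), and does not evaluate DLTs (Section 7.6).

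The restart option may also be limited for these subjects. Footnote 2 of Table 5-3 says reduction is not possible at 50 mg BID, the starting level. That both subjects are at that level is an inference from the enrollment of two in a cohort needing at least three evaluable subjects. The pneumonitis row, as it reads here, does not cite the footnote.

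**Conclusion.** The point stands as an inconsistency of classification. Section 5.7.4 can be read to place an asymptomatic imaging-only finding in Grade ≥ 2, while Table 5-3 places asymptomatic pneumonitis in Grade 1. The table heading also disagrees with its own first row.

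The consequence for an affected subject is large: a required permanent stop of both drugs, against a hold of one with the other continuing. The reach is small: at most the two enrolled subjects, with a probability that the documents do not allow anyone to estimate.

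The conclusion rests on three assumptions: the ordinary reading of and/or, a finding that arises during combination therapy, and the absence of a precedence rule elsewhere in the two documents. It takes no view on which classification is clinically right. It should be corrected because it bears on subject safety and the correction is simple.

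**What to change.** Reconcile Section 5.7.4 with the pneumonitis block of Table 5-3:

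1. Use one description of Grade 1 and one of Grade ≥ 2 in both places, with the and/or resolved so that imaging change without symptoms falls in one grade only.
2. Reword the block heading in Table 5-3 so that it covers its asymptomatic row.
3. State the resulting action for idelalisib and for BI 836826 in both places, in agreement with the linked-discontinuation rule in Section 5.6.

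The sponsor decides which classification and actions apply. The cost is wording in one paragraph and one table heading, with no added procedure, assessment or analysis. As a protocol modification it would need the IRB/IEC submission and approval described in Section 9.2.1.

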5.7.5. Hematological and Immunological Events

In the Phase 1 experience with idelalisib in patients with NHL and CLL, subjects with Grade ≥ 3 neutropenia, anemia, and/or thrombocytopenia were enrolled to clinical trials. Decreased levels of neutrophil counts, hemoglobin, or platelet counts during idelalisib administration were largely due to minor fluctuations in these parameters among subjects with pre-existing hematological abnormalities due to disease or prior therapy. Thus, idelalisib did not appear to induce overt myelosuppression. Obvious patterns of drug-mediated reductions in circulating CD4+ lymphocyte counts or suppression of serum IgG levels were also not observed.

Treatment-emergent Grade 3 or 4 neutropenia events, including those accompanied by fever or infection, have occurred in subjects treated with idelalisib. All subjects should have their blood counts monitored at least every 2 weeks for the first 6 months of idelalisib treatment. For subjects who develop neutropenia Grade 3, blood counts must be monitored at least weekly until neutropenia is Grade ≤ 2 . For subjects who develop neutropenia Grade 4, idelalisib must be interrupted and blood counts monitored at least weekly until neutropenia is Grade ≤ 2 . Idelalisib dosing may be resumed at lower dose level when neutropenia is Grade ≤ 3 . Neutropenia should be managed according to established clinical guidelines.

No modification of either study drug for changes in circulating CD4+ counts or Ig levels is planned.

